FACIT-Fatigue [®]	Functional assessment of chronic illness therapy fatigue scale
FAS	Full Analysis Set
GGT/γGT	Gamma glutamyl transferase
HAQ-DI [®]	Health assessment questionnaire – disability index
HDL	High density lipoprotein
HGB	Hemoglobin
HR-QoL	Health-related quality of life
ICF	Informed consent form
IL	Interleukin
IRT	Interactive response technology
i.v.	Intravenous(ly)
LDL	Low density lipoprotein
LFT	Liver function test
LLN	Lower limit of normal
LOCF	Last observation carried forward

MedDRA	Medical Dictionary for Drug Regulatory Affairs
MRMM	Mixed-effects repeated measures model
	
MRI	Magnetic resonance imaging
MTX	Methotrexate
NMQ	Novartis MedDRA Queries
NSAID	Non-steroidal anti-inflammatory drug
PD	Protocol Deviation
PFS	Prefilled syringe
PsA	Psoriatic arthritis
PPS	Per-protocol set
PSOC	Primary system organ class
PT	Preferred term
QFT	QuantiFERON tuberculosis gold test
RAN	Randomized set
SAE	Serious adverse event
SAF	Safety set
SAP	Statistical Analysis Plan
s.c.	Subcutaneous(ly)
SCC	Squamous cell carcinoma
SMQ	Standardised MedDRA Queries
SOC	System Organ Class
SPARCC	Spondyloarthritis Research Consortium of Canada
SPP	Safety Profiling-Plan
TB	Tuberculosis
TBL	Total bilirubine
TNF	Tumor necrosis factor
ULN	Upper limit of normal
VAS	Visual analog scale
WBC	White blood cells

1 Introduction

This document describes the planned statistical methods for all safety and efficacy analyses, which will be used in the phase IIIb clinical trial AIN457F3302.

The main purpose of this document is to provide summary of the statistical methodology that will be used for this clinical study; this includes a detailed description of data summaries. Analyses plan in this document refers to the related statistical analysis sections in clinical study report.

Data will be analyzed by Novartis using statistical software SAS version 9.4 according to the data analysis section 9 of the study protocol, which is available in Appendix 16.1.1 of the CSR. That statistical methodology is described below and any deviations from the protocol are documented. Additional detailed information regarding the analysis methodology is contained in the Appendix section 16.1.9 of CSR.

Please refer to the following document:

Clinical Protocol CAIN457F3302

1.1 Study design

This is a 52-week, randomized, double-blind, double-dummy, placebo-controlled, multicenter study to assess the efficacy of secukinumab 150 mg or 300 mg in patients with AxPsA who have had an inadequate response to two different NSAIDs. The study will consist of two treatment periods; a double-blind placebo-controlled period from Baseline to Week 12 followed by a double-blind secukinumab treatment period from Week 12 to Week 52.

The schematic of study design is given in Figure 1.1 below.

Planned number of patients and randomization

A total of 495 patients (165 patients per group) will be recruited to compensate dropouts and protocol violators.

Patient eligibility will be assessed during a maximum screening period of 8-weeks. At Baseline, all patients whose eligibility is confirmed will be randomized in a 1:1:1 ratio to secukinumab 150 mg, secukinumab 300 mg or placebo. At Week 12, patients randomized to placebo at Baseline will be re-randomized (1:1) to active treatment with secukinumab 150 mg or secukinumab 300 mg.

Group 1: secukinumab 150 mg

Treatment Period 1

secukinumab 150 mg (1 × 1.0 mL prefilled syringes (PFS)) + placebo (1 × 1.0 mL PFS) at Baseline, Week 1, 2, 3 and 4, then 4 weeks later at Week 8.

Treatment Period 2

secukinumab 150 mg (1 × 1.0 mL PFS) + placebo (1 × 1.0 mL PFS) administered every 4 weeks from Week 12 to Week 52 (last dose on Week 48).

Group 2: secukinumab 300 mg

Treatment Period 1

secukinumab 300 mg (2 × 1.0 mL PFS) administered at Baseline, Week 1, 2, 3 and 4, then 4 weeks later at Week 8.

Treatment Period 2

secukinumab 300 mg (2 × 1.0 mL PFS) administered every 4 weeks from Week 12 to Week 52 (last dose on Week 48).

Group 3: placebo

Treatment Period 1

placebo (2 × 1.0 mL PFS) administered at Baseline, Week 1, 2, 3 and 4, then 4 weeks later at Week 8.

Treatment Period 2

secukinumab 150 mg (1 × 1.0 mL PFS) + placebo (1 × 1.0 mL PFS) administered every 4 weeks from Week 12 to Week 52 (last dose on Week 48), OR

secukinumab 300 mg (2 × 1.0 mL PFS) administered every 4 weeks from Week 12 to Week 52 (last dose on Week 48).

[figure not shown]
Patients, investigator staff, persons performing the assessments and data analysts will remain blinded to the identity of the treatment from the time of randomization until database lock. No stratification at randomization will be performed.

Primary analysis time point

The primary and key secondary analyses will be performed at Week 12.

Figure 1.1: Study Design

[figure not shown]
1.2 Study objectives and endpoints

[figure not shown]
Table 1.2-1 Objectives and related endpoints

Objective	Endpoint
Primary objective	
To demonstrate that secukinumab 300 mg s.c. is superior to placebo in the achievement of ASAS 20 response at Week 12.	Proportion of patients with ASAS 20 response at Week 12
Key secondary objective	
To demonstrate that secukinumab 150 mg s.c. is superior to placebo in the achievement of ASAS 20 response at Week 12 after superiority of 300 mg is established	Proportion of patients with ASAS 20 response at Week 12, after superiority of 300 mg is established

Secondary objectives	
To evaluate secukinumab 300 mg s.c. versus placebo in the achievement of ASAS 40 at Week 12	Proportion of patients with ASAS 40 response at Week 12
To evaluate secukinumab 150 mg s.c. versus placebo in the achievement of ASAS 40 at Week 12	
To evaluate secukinumab 300 mg s.c. versus placebo in the achievement of BASDAI 50 at Week 12	Proportion of patients with BASDAI 50 response at Week 12
To evaluate secukinumab 150 mg s.c. versus placebo in the achievement of BASDAI 50 at Week 12	
To evaluate secukinumab 300 mg s.c. versus placebo in the reduction of spinal pain measured by visual analog scale (VAS) at Week 12	Mean change from baseline of spinal pain assessed by VAS at Week 12
To evaluate secukinumab 150 mg s.c. versus placebo in the reduction of spinal pain measured by VAS at Week 12	
To evaluate secukinumab 300 mg s.c. versus placebo in achieving an improvement in Spondyloarthritis Research Consortium of Canada (SPARCC) enthesitis index at Week 12	Mean change from baseline of SPARCC enthesitis index at Week 12.
To evaluate secukinumab 150 mg s.c. versus placebo in achieving an improvement in SPARCC enthesitis index at Week 12	
To evaluate secukinumab 300 mg s.c. versus placebo in achieving an improvement in health assessment questionnaire disability index (HAQ-DI [©]) at Week 12	Mean change from baseline of health assessment questionnaire disability index (HAQ-DI [©]) at Week 12.
To evaluate secukinumab 150 mg s.c. versus placebo in achieving an improvement in HAQ-DI [©] at Week 12	
To evaluate secukinumab 300 mg s.c. versus placebo in achieving an improvement in the functional assessment of chronic illness therapy fatigue scale (FACIT-Fatigue [©]) at Week 12	Mean change from baseline of functional assessment of chronic illness therapy fatigue scale (FACIT-Fatigue [©]) at Week 12
To evaluate secukinumab 150 mg versus placebo in achieving an improvement in the FACIT-Fatigue [©] at Week 12	

To evaluate secukinumab 300 mg s.c. versus placebo in achieving an improvement in the ASAS health index at Week 12	Mean change from baseline of ASAS health index at Week 12
To evaluate secukinumab 150 mg s.c. versus placebo in achieving an improvement in the ASAS health index at Week 12	
To evaluate secukinumab 300 mg s.c. versus placebo based on the proportion of patients achieving an ACR 20 response at Week 12	Proportion of patients with ACR 20 response at Week 12
To evaluate secukinumab 150 mg s.c. versus placebo based on the proportion of patients achieving an ACR 20 response at Week 12	
To evaluate the safety and tolerability of secukinumab	Overall safety, as measured by frequency and severity of adverse events and changes in laboratory, vital signs and ECG values from baseline

2 Statistical methods

2.1 Data analysis general information

The data will be analyzed by Novartis and/or by the designated CRO. It is planned that the data from all centers that participate in this protocol will be used for analysis. Analysis datasets and statistical outputs will be produced using the most recent SAS® Version 9.4 (SAS Institute Inc., Cary, NC, USA), and stored in Novartis global programming & statistical environment (GPS).

As the primary endpoint analysis will be performed at Week 12, there will be a database freeze after all patients have completed Week 12 assessments. A selected Novartis clinical team will be unblinded to the Week 12 results. Summary results may be shared internally and externally; however, individual unblinded patient data will not be disclosed. A final database lock will occur when all patients have completed the study.

Summary statistics for continuous variables will include number of patients (N), mean, standard deviation, minimum, lower quartile, median, upper quartile, maximum. Summary statistics for discrete variables will be presented in the number and percent of patients in each category. Summary statistics will also be presented graphically wherever applicable.

If not otherwise specified, p-values and confidence interval (CI) will be presented as two-sided. Unless otherwise stated, the default level of significance will be set to 5% (two-sided, family-wise type-I-error).

Data analyses will be presented by treatment group. Efficacy and safety data for the placebo-controlled period (or the entire treatment period as appropriate) will be presented by the following 3 treatment groups. Patients may be included in more than one treatment group for some analyses (e.g. exposure-adjusted adverse events over the entire treatment period).

Eligible patients will be randomized to secukinumab 150 mg (Group 1), secukinumab 300 mg (Group 2) or placebo (Group 3) for the first 12 weeks. Note that the treatment groups for a patient may differ depending on the time period of the analysis and whether one assesses the patient for efficacy or safety.

The analysis will be conducted on all patients' data at Week 12 and at the time, the trial ends (Week 52).

Comparative efficacy data

Comparative efficacy analyses (i.e. inferential efficacy comparisons with placebo) will focus on the time period when both active drug and the placebo are given in a manner suitable for making comparisons (i.e., first 12-weeks of treatment). Comparative efficacy will be performed based on the FAS population using the randomized treatment. After week 12 till week 52, the efficacy endpoints will be summarized descriptively or otherwise specified using inferential analysis, on the FAS population.

2.1.1 General definitions

Study treatment: Study treatment refers to:

Secukinumab 150 mg provided in 1 ml PFS or Secukinumab placebo provided in 1 ml PFS.

Study treatment start and end date: Study treatment start date is defined as the first date when a non-zero dose of study drug is administered and recorded on the Drug Administration Record (DAR) CRF page. Similarly, study drug end date is defined as the last date when a non-zero dose of study drug is administered and recorded on the DAR CRF page of the core study.

Study day: Study day will be calculated as (event date – study drug start date + 1 day) for events that occurred on or after study drug start date (e.g., visit, lab samples, AEs). For events prior to study drug start date (e.g., time of diagnosis), study day will be negative and calculated as (event date – study drug start date). Note that study drug start date is study day 1 and the day before study drug start date is study day -1 (i.e. no study day 0).

Due to the study drug dosing schedule, one month will be considered as 28 days. However, for “time since event” data (e.g., medical history), one month will be considered as 365.25/12 days for events that occurred prior to study Day 1. Time from events prior to the start of study drug, e.g., time since diagnosis, is calculated as the difference between the start date of study drug and the date of prior event.

Note that, the first dose day is Day 1, and the day before the first dose day is counted as Day -1 (not Day 0).

Baseline and post baseline: In general, a *baseline* value refers to the last measurement made prior to administration of the first dose of study treatment. A post-baseline value refers to a measurement taken after the first dose of study treatment.

Treatment Period: There are 2 treatment periods for this study defined as:

Treatment Period 1 is defined as a 12 Week placebo-controlled, double-blind treatment period starting from baseline till Week 12.

Treatment Period 2 is a 40 Week double-blinded active treatment period starting from Week 12 till Week 52.

Lost to follow up: The patients, whose study completion status is unclear, because they fail to appear for study visits without stating an intention to withdraw.

On-treatment period: The period where the patients are exposed to the study treatment. For this study, the treatment phase consists of 52 weeks. For this study, the treatment phase consists of 52 weeks (for treatment group 1 or group 2) for secukinumab, and 12 weeks of on-treatment period for placebo and 40 weeks of on treatment for secukinumab (for treatment group 3).

2.1.2 Visits windows

Visit-windows will be used for the data that is summarized by visit; they are based on the study evaluation schedule and comprise a set of days around the nominal visit day. For any assessment, there are the protocol defined scheduled visits around which visit windows were created to cover the complete range of days within the study. The visit windows are shown in [Table 2-1](#). These apply to measurements taken at every visit. For assessments, collected less often different visit windows will be applied as detailed below.

When visit windows are used, all visits will be re-aligned, i.e., they will be mapped into one of the visit windows. E.g., if the *Week 4* visit of a subject is delayed and occurs on Day 46 instead of on Day 29, say, it will be re-aligned to visit window *Week 8*. In the case of major deviations from the visit schedule, or due to unscheduled visits, several assessments of a subject may fall in a particular visit window (either scheduled or unscheduled). Statistical approaches to handle multiple assessments in a given visit window are specified below.

Of note, subjects are allowed to have gaps in visits.

Table 2-1 Assessment windows for scheduled visits

Analysis Visit	Week	Scheduled Day	Visit Window
Baseline	BSL	1	-28 days to Day 1*
Week 1	1	8	Day 2-11
Week 2	2	15	Day 12-18
Week 3	3	22	Day 19-25
Week 4	4	29	Day 26-43
Week 8	8	57	Day 44-71
Week 12	12	85	Day 72-104
Week 16	16	113	Day 105-141
Week 24	24	162	Day 142-183
Week 32	32	218	Day 184-253
Week 40	40	289	Day 254-323
Week 48	48	337	Day 324-351
Week 52	52	365	Day 352 onwards

* Baseline measurement before the first drug administration for safety assessments and before the randomization for efficacy assessments. For efficacy visit windows, refer to date of randomization.

For parameters, which are not collected at every visit (e.g., FACIT-Fatigue©, HAQ-DI©), visit windows defined in [Table 2-4](#) will be combined. For example, if a parameter is measured at Week 12 and Week 24 only, Week 12 visit window will extend from Day 2 to Day 104 (combining Week 1 to Week 12 visit windows), Week 24 will extend from Day 105 to Day 183 (combining Week 16 to Week 24). If more than one assessment falls into the interval, the rules defined in [Section 2.1.3](#) below are applied.

Table 2-4a Drug administration windows for scheduled visits of Exposure Data

The administration of study drug at weeks 20, 28, 36, and 44 is not in relation to a study visit. For exposure data, a specific assessment window for those weeks is used in order to account for the home administrations at those weeks.

Analysis Visit	Week	Scheduled Day	Visit Window
Baseline	BSL	1*	
Week 1	1	8	Day 2-11
Week 2	2	15	Day 12-18
Week 3	3	22	Day 19-25
Week 4	4	29	Day 26-43
Week 8	8	57	Day 44-71
Week 12	12	85	Day 72-99
Week 16	16	113	Day 100-127
Week 20	20	141	Day 128-155
Week 24	24	169	Day 156-183
Week 28	28	197	Day 184-211
Week 32	32	225	Day 212-239
Week 36	36	253	Day 240-267
Week 40	40	281	Day 268-295
Week 44	44	309	Day 296-323
Week 48	48	337	>= 324 Days

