2.1.3 Multiple assessments within visit windows

When there are *multiple assessments* in a particular visit window, the following rules are applied to select one value “representing” the subject in summary statistics in a visit window (See [Table 2-2](#)).

For baseline assessment definition, see [Section 2.1.1](#). For post-baseline visit windows, the following applies (unless otherwise specified):

- for *quantitative variables*, the *closest* to the actual visit is chosen (if two assessments have the same distance, then the earlier one will be chosen);
- for *qualitative variables*, the *worst* record is selected. It is noted that in the analyses performed, *worst* case is always well defined.
- in case qualitative variables are based on quantitative variables, e.g. ACR 20 response, the visit will be assigned to the quantitative variable, and this visit will be used for the derived qualitative variable.

Table 2-2 Rules for selecting values for analysis

Timing of measurement	Type of data	Rule
Baseline	All data	
The last non-missing measurement made prior to or on the date of administration of the first dose of study treatment (the reference start date / Day 1). If a patient did not receive any dose of study treatment, then the randomization date will be used. Only date part is considered if just one assessment on Day 1.
 
If there are multiple assessments on Day 1, following rules will apply:
 
a. If assessment time exists,
• select the last available measurement prior to reference start date/time considering time;• if no measurement prior to reference start date/time considering time, select the earliest measurement post reference start date/time considering time.b. If assessment time does not exist, select the available measurement from the lowest CRF visit number.

Timing of measurement	Type of data	Rule
Post-baseline efficacy	All data	
The measurement closest to the target day will be used. In the event two measurements are taken equally apart (e.g., 1 day before target date and 1 day after), the earlier one will be used.
 
Cases where the same parameter is recorded more than once on the same date will be handled as follows:
 
 • If time of completion exists, the earliest measurement will be used; • If time does not exist, the measurement from the lowest CRF visit number will be used.

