5.6.1 Secondary analyses

Categorical variables will be analyses using the logistic model, code is described above.

Endpoints with continuous data type expected to be normally distributed will be analyzed using an analysis of covariance (ANCOVA) model with treatment and baseline stratification factor, and baseline value as covariate. Confidence intervals for the difference between each dose of secukinumab and placebo will be calculated.

SAS code for ANCOVA

```
proc mixed data=aaa;
class TRT STRATA;
model response = TRT STRATA BASE / s;
lsmeans TRT / diff;
run;
```

In addition, key secondary variables measured at all post baseline visits up to Week 52 will be analyzed using longitudinal mixed effects ANCOVA model with treatment, baseline stratification factor and analysis visit as factors; and weight, baseline value, treatment by visit and baseline by visit interactions as covariates. An unstructured covariance structure will be assumed for this model. The significance of the treatment effects for secukinumab regimens at different analysis visits will be determined from the pairwise comparisons performed between secukinumab regimens and placebo at the appropriate analysis visits.

SAS code for mixed model:

```
proc mixed data=aaa;
class TRT USUBJID AVISITN STRATA;
model CHG=TRT STRATA AVISITN WEIGHT BASE TRT*AVISITN BASE*AVISITN
/ s ddfm=kr;
lsmeans TRT*AVISITN / diff cl;
repeated AVISITN / type=un subject=USUBJID;
Run;
```

In case the MMRM model does not converge the following sequential steps will be used:

1. change ddfm=kr to ddfm=bw. If still no convergence, perform step 2.
2. change type=un to type=cs. If still no convergence, perform step 3.

3. remove covariates in the following order until convergence: WEIGHT, BASE*AVISITN, STRATA.

Crude and adjusted incidence rates

The SAS codes of crude and adjusted incidence rates and confidence intervals will be referred from the MAP or AIN457F2310 M3.

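### Table 2-1 prints Scheduled Days 162, 218 and 289 for Weeks 24, 32 and 40, where the SAP's own day convention and Table 2-4a give 169, 225 and 281

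*SAP*

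**What the plan says.** - **Day numbering.** SAP section 2.1.1: "Note that study drug start date is study day 1". There is no Day 0. The footnote to Table 2-1 counts efficacy windows from the randomization date instead.
- **Assessment windows.** Section 2.1.2 describes windows that "comprise a set of days around the nominal visit day". Table 2-1 lists Week 24 at Scheduled Day 162 (window Day 142-183), Week 32 at 218 (184-253) and Week 40 at 289 (254-323).
- **Exposure windows.** Table 2-4a, in the same section and with the same column heading, lists these weeks at 169, 225 and 281. It has extra rows because "The administration of study drug at weeks 20, 28, 36, and 44 is not in relation to a study visit".
- **Choice among several values.** Table 2-2 in section 2.1.3, for post-baseline efficacy: "The measurement closest to the target day will be used". A tie goes to the earlier value. The general rule for quantitative variables in the same section is worded differently: the value closest "to the actual visit is chosen".
- **Use of the late visits.** Section 2.1: "After week 12 till week 52, the efficacy endpoints will be summarized descriptively or otherwise specified using inferential analysis".

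**The concern.** One SAP gives two different nominal days for each of three visits. For the assessment windows this number has a job. Section 2.1.2 expects that unscheduled or badly timed visits can put several assessments in one window, and Table 2-2 settles the choice by distance to a target day. If a programmer takes the target from Table 2-1, the value shown for Week 24, 32 or 40 can be one taken up to two weeks off schedule, although the patient also has a value on the right day.

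**Working it through.** **Inputs.** Scheduled Days and windows from Tables 2-1 and 2-4a; Day 1 convention from section 2.1.1; selection and tie rule from Table 2-2.

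**1. Can the printed days be reproduced?** With Day 1 as the start, the nominal day of Week w is 7w + 1.

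| Week | 7w + 1 | Table 2-1 | Table 2-4a | Table 2-1 error |
|---|---|---|---|---|
| 12 | 85 | 85 | 85 | 0 |
| 16 | 113 | 113 | 113 | 0 |
| 24 | 169 | 162 | 169 | -7 |
| 32 | 225 | 218 | 225 | -7 |
| 40 | 281 | 289 | 281 | +8 |
| 48 | 337 | 337 | 337 | 0 |
| 52 | 365 | 365 | no row | 0 |

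Weeks 1, 2, 3, 4 and 8 (Days 8, 15, 22, 29, 57) also fit in both tables. So 9 of the 12 post-baseline rows of Table 2-1 and all 15 of Table 2-4a follow the rule, and the three rows in question do not. Day 162 is Week 23 (161/7) and Day 218 is Week 31 (217/7).

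**2. Which set do Table 2-1's own edges fit?** The Week 16 window ends on Day 141. The midpoint with the correct Week 24 day is (113 + 169)/2 = 141; with the printed day it is (113 + 162)/2 = 137.5. The Week 32 window ends on Day 253, and (225 + 281)/2 = 253; the printed days give (218 + 289)/2 = 253.5.

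**3. Possible origin.** The window centres are (142 + 183)/2 = 162.5, (184 + 253)/2 = 218.5 and (254 + 323)/2 = 288.5. The printed days look like rounded centres. This suggests a source for the slip but does not prove one.

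**4. Effect on selection.** Take a value exactly on schedule and ask which second value in the same window would replace it, using the printed target and giving ties to the earlier value.

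- Week 24: |169 - 162| = 7. Days 156-168 are closer; Day 155 ties and is earlier. Displacing days: 155-168 (14 days).
- Week 32: |225 - 218| = 7. Days 212-224 are closer; Day 211 ties and is earlier. Displacing days: 211-224 (14 days).
- Week 40: |281 - 289| = 8. Days 282-296 are closer; Day 297 ties but is later, so it loses. Displacing days: 282-296 (15 days).

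Example: with values on Days 158 and 169, the distances to 162 are 4 and 7, so Day 158 represents Week 24. With target 169 the distances are 11 and 0, and Day 169 is chosen.

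**5. Window edges, checked separately.** The edges after Days 183 and 323 are midpoints in Table 2-4a, which has Week 28 and Week 44 rows: (169 + 197)/2 = 183 and (309 + 337)/2 = 323. Between the neighbouring assessment visits, the midpoints on the correct days are (169 + 225)/2 = 197 and (281 + 337)/2 = 309. Days 184-196 are thus filed under Week 32 though nearer Week 24, and Days 310-323 under Week 40 though nearer Week 48. Visits held on the nominal day fall in the right window.

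**The case against.** Several points on the other side have force.

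- **The target day is never defined.** Table 2-2 does not tie it to the Scheduled Day column, and the general rule speaks of the actual visit. This stands in part: the reading used here is the likely one, not a certain one. No other column offers a target for assessments, and a programmer who takes the days from Table 2-4a has already corrected the table.
- **Lying near the window centre proves nothing.** This stands. Weeks 2, 3, 8 and 48 are also within half a day of their window centres and are correct nominal days. The error rests on the mismatch with 7w + 1 and with Table 2-4a.
- **Efficacy windows count from randomization, not first dose.** True, but it moves the origin and not the spacing, so the arithmetic is the same.
- **Week 52 inference.** A reader might infer that inferential results are distorted, because section 5.6 says "key secondary variables measured at all post baseline visits up to Week 52 will be analyzed using longitudinal mixed effects ANCOVA model". The document does not support that. The only key secondary variable is binary ASAS 20 response at Week 12, while the code models a change score. The comparisons described are against placebo, which ends at Week 12.
- **Patient-reported outcomes.** A reader might infer that all of them are affected at these weeks. HAQ-DI and FACIT-Fatigue are not collected at every visit and use combined windows, and the SAP does not give their collection weeks. Whether these rows apply to them is unknown.
- **Edges.** A reader might infer that the window edges are wrong as well. The SAP states no midpoint rule and says outright that a late visit is re-aligned to a neighbouring window. The edges break no stated rule.

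**Conclusion.** The three Scheduled Days are wrong as written: they contradict the SAP's day convention and its own exposure table by -7, -7 and +8 days. Severity is minor. The consequence arises only when a patient has two or more efficacy values in the Week 24, 32 or 40 window, and it rests on the assumption that the target day is the Scheduled Day of Table 2-1. What is affected is mainly descriptive by-visit efficacy output at those weeks. The number of patients cannot be derived from the document. The Week 12 row (Day 85) is correct, so the primary and key secondary analyses are not affected. The window edges are a matter for an optional remark and not an error.

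**What to change.** In Table 2-1, set the Scheduled Days for Weeks 24, 32 and 40 to 169, 225 and 281. In Table 2-2, state that the target day is the Scheduled Day of Table 2-1. The cost is three numbers and one sentence, with no change to the conduct of the trial.

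Optional: the sponsor may wish to re-centre the late windows on the assessment visits, for example Day 142-197, 198-253, 254-309 and 310-351 for Weeks 24, 32, 40 and 48. The worked example in section 2.1.2 ("Week 24 will extend from Day 105 to Day 183") would then need to end at Day 197. The correction does not depend on this.
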